## 1.3.2. Visits on Day 1 of Every Other Cycle (up to 35 cycles and >35 cycles)

Visit Identifier	Visits on Day 1 of Every Other Cycle up to 35 cycles (up to 24 months)	Visits on Day 1 of Every Other Cycle (> 35 cycles or 24 months)	Notes  (X) refer to specific footnote when the measurement may be optional /repeat measurement might not be required.
Visit Window	±4 days	±4 days	
Physical examination	X		
Weight	X		
Contraception check (as	X	X	At cycle not requiring site visit the participant may be contacted by phone to
appropriate)	(every cycle ±2 days)	(every cycle ±2 days)	confirm contraception is still appropriate per the protocol.
Laboratory			

Visit Identifier	Visits on Day 1 of Every Other Cycle up to 35 cycles (up to 24 months)	Visits on Day 1 of Every Other Cycle (> 35 cycles or 24 months)	Notes  (X) refer to specific footnote when the measurement may be optional /repeat measurement might not be required.
Visit Window	±4 days	±4 days	
Pregnancy test	X (every cycle ±2 days)	X (every cycle ±2 days)	Pregnancy tests will be routinely repeated at every cycle (±2 days) during the active treatment period and additionally whenever one menstrual cycle is missed or when potential pregnancy is otherwise suspected. The pregnancy test should be performed at the clinical site's local laboratory. Where that is not possible, participants will provide the laboratory test results carried out at a non-clinical site laboratory, eg, by telephone, and bring a copy of the laboratory test results at the next cycle visit. The copy of the laboratory test results must be retained in the participants' file at the clinical site for documentation purposes.
Study Intervention			
Study Intervention	Once a day continuously		
Tumor Assessments			
CT and MRI Scan or Equivalent	(every 6 weeks ± 1 week)	(As per local clinical practice)	CT and MRI scans to be done at every 6 weeks ±1 week up to approximately 24 months (cycle 35) and then as per local clinical practice.
Other Clinical Assessments			
Adverse Events	X	X	
Concomitant medications and non-drug supportive interventions	X		All concomitant medications and non-drug supportive interventions should be recorded in the CRF until the participant has completed 35 cycles of treatment (approximately 24 months). After cycle 35 the data will be reported in the medical chart, but not collected in the CRF.

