	• Using the Kaplan-Meier method, estimate its associated statistics on TTP (including the median TTP with two-sided 95% CI, the TTP rates at clinically meaningful timepoints with two-sided 95% CI) for all participants who received at least one dose of lorlatinib without regard to discontinuation from treatment unless death occurs, new anti-cancer therapy is initiated or extended gap in tumor assessment is present prior to progression. TTP is defined as the time from date of first dose to the date of the first documented PD.				
	This analysis is based on ITT population. Participants with an event more than 12 weeks (24 weeks post the first 42 weeks) after the last adequate tumor assessment will be censored on the date of the last adequate tumor assessment prior to the gap that documented no progression. If the participant dies before progression, the participant will be censored on the date of death. If a new anticancer therapy starts prior to an event, the participant will be censored on the date of the last adequate tumor assessment that				

Endpoint	Statistical Analysis Methods				
	documented no progression prior to start of the new anti-cancer therapy. Participants with inadequate baseline assessment or with a adequate post-baseline tumor assessments within 12 weeks after the start date will be censored on the start date, unless the participant dies within 12 weeks of the start date, in which case, the patient who be censored on date of death. The CI for the median TTP will be calculated according to Brookmeyer and Crowley method, and the CIs for the survival function estimates at the timepoints will be derived using the log(-log) method.				
	PFS by ICR/INV				
	• Using the Kaplan-Meier method, estimate its associated statistics of PFS (including the median PFS with two-sided 95% CI, the PFS rates at clinically meaningful timepoints with two-sided 95% CI) for all participants who received at least one dose of lorlatinib without regard to discontinuation from treatment unless new anti-cancer therapy is initiated or an extended gap in tumor assessment is present prior to progression or death. PFS is defined as the time from date of first dose to the date of the first documented PD or death due to any cause, whichever occurs first.				

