	This analysis is based on ITT population. Participants with an event more than 12 weeks (24 weeks post the first 42 weeks) after the last adequate tumor assessment will be censored on the date of the last adequate tumor assessment prior to the gap that documented no progression. If a new anti-cancer therapy starts prior to an event, the participant will be censored on the date of the last adequate tumor assessment that documented no progression prior to start of the new anti-cancer therapy. Participants with inadequate baseline assessment or with no adequate post-baseline tumor assessments within 12 weeks after the start date will be censored on the start date, unless the participant dies within 12 weeks of the start date, in which case, death will be an event on date of death. The CI for the				
	median PFS will be calculated according to Brookmeyer and Crowley method, and the CIs for the survival function estimates at the timepoints will be derived using the log(-log) method.				

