6.2.7. PFS by ICR/INV

Analysis set: ITT: All enrolled participants who take at least 1 dose of Lorlatinib

Analysis methodology:

PFS is defined as the time from date of first dose to the date of the first documentation of PD per RECIST v1.1 as assessed by ICR/INV or death due to any cause, whichever occurs first and will be summarized in months:

PFS (months) = [date of event or censoring-date of treatment start +1]/30.4375.

PFS data will be censored as follows:

- For participants who start a new anti-cancer therapy prior to an event, censoring will be at the last adequate tumor assessment (see Section 5.2.9) prior to the start of new anti-cancer therapy. Note: if date of progression occurs on the same date as the start of new anti-cancer therapy, the progression will be counted as an event.
- For participants with documented progression or death after two or more missing tumor assessments, censoring will occur at the last adequate tumor assessment prior to the missing assessments. In this study antitumor activity will be assessed through radiological tumor assessments conducted at screening and every 6 weeks until disease progression regardless of initiation of subsequent anti-cancer therapy. The allowable time window for disease assessments is ±1week while on treatment and whenever disease progression is suspected (eg, symptomatic deterioration). Therefore time without adequate assessment is defined as 98 days (12 weeks plus 2 weeks).
- For participants who do not have an adequate baseline tumor assessment or who do not have any post-baseline tumor assessments, censoring will occur on the date of first dose unless death occurred on or before the time of the second planned tumor assessment (ie, on or before day 98) in which case the death will be considered an event. Note for participants who died without any post baseline assessments and meet the definition of two or more missing assessment the reason for censoring will be documented as two or more missed assessments and censoring will occur on the date of first dose.
- All other participants alive without objective progression will be censored on the date of the last adequate tumor assessment.

DMB02-GSOP-RF02 4.0 Statistical Analysis Plan Template 01-Nov-2018 PFIZER CONFIDENTIAL Page 28 TMF Doc ID: 98.03 The date of tumor response at each nominal timepoint based on the ICR/INV assessments will be used for determining the dates of last adequate assessment for censoring purposes.

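### Protocol 9.4.1 censors PFS and TTP on day 1 when no adequate scan falls within 12 weeks, even if later scans document progression; the SAP has no such rule, and neither document clearly governs

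*Protocol*

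**What the plan says.** Protocol 9.4.1, PFS: participants "with no adequate post-baseline tumor assessments within 12 weeks after the start date will be censored on the start date". The one exception is an early death, which counts as an event if it falls in that period. Nothing is said about adequate scans after week 12.

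Protocol 9.4.1, TTP: the cell also has "adequate post-baseline tumor assessments within 12 weeks after the start date will be censored on the start date". The word before this phrase is damaged in the text available and is read here as a negative, the only reading that makes sense. Deaths within 12 weeks are censored at death.

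A separate sentence in both cells is the gap rule: an event "more than 12 weeks (24 weeks post the first 42 weeks) after the last adequate tumor assessment will be censored" at that last assessment.

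The imaging schedule (Protocol 1.3.2 and 8.1.1) is "CT and MRI scans to be done at every 6 weeks ±1 week up to approximately 24 months".

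SAP 6.2.7 and 6.2.8 censor at first dose when the baseline is inadequate, or for participants "who do not have any post-baseline tumor assessments, censoring will occur on the date of first dose unless death occurred" by day 98. They have no 12-week condition. The gap threshold is 98 days. SAP Tables 2 and 4 measure it from first dose when there is no earlier adequate post-baseline scan.

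**The concern.** The 12-week sentence is not a rule about an event that follows a long unobserved interval. It looks only at whether an adequate scan exists by day 84. If none does, it discards everything seen afterwards, including regular scans and a documented progression. Its limit also falls inside the window for the second scheduled scan.

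Two things are at stake. First, valid follow-up and valid progressions are lost from PFS and TTP. The effect on the estimates can go either way, since both long progression-free times and early progressions are removed. Second, the protocol's ORR and DoR analyses have no matching condition, so under the protocol one participant can have a confirmed response, a DoR ending in progression, and a PFS censored on day 1. A programmer working from the SAP and one working from the protocol would build different PFS and TTP datasets.

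**Working it through.** **Inputs.** Scans every 6 weeks ±1 week (Protocol 1.3.2); 12-week start-date rule, 12-week gap rule and 24-week gap rule after week 42 (Protocol 9.4.1); 98-day gap rule and time formula (SAP 6.2.7, Table 2); 70 participants (Protocol 9.2). Days are counted from first dose.

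**The SAP's own figure.** 12 × 7 + 2 × 7 = 98 days, as stated.

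**Scan windows.** Scan 1: 42 ± 7 = days 35–49. Scan 2: 84 ± 7 = days 77–91. The protocol limit is 12 × 7 = 84 days, so days 85–91 are in window for scan 2 but past the limit.

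**Scan histories under each rule.** Months = (days from first dose to event or censoring + 1)/30.4375, so censoring at the start gives 1/30.4375 = 0.03 months.

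| Case | Protocol 9.4.1 | SAP 6.2.7 |
|---|---|---|
| A. All scans adequate, at the latest allowed dates (days 49, 91, 133 …), PD day 259 | event, 8.54 | event, 8.54 |
| B. Scan 1 missed or not evaluable, scan 2 on day 84, PD day 252 | event, 8.31 | event, 8.31 |
| C. Scan 1 missed or not evaluable, PR day 91, confirmed day 126, PD day 252 | censored, 0.03 | event, 8.31 |
| D. Scan 1 missed or not evaluable, PD day 91 | censored, 0.03 | event, 3.02 |
| E. Scans 1 and 2 missing, PR day 126, confirmed day 168, PD day 252 | censored, 0.03 | event, 8.31 |
| F. Scans 1 and 2 missing, PD day 126 | censored, 0.03 | censored, 0.03 |

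These histories contain no deaths, so TTP gives the same results. In case C, time to response is (91 + 1)/30.4375 = 3.02 months and DoR is (252 − 91 + 1)/30.4375 = 5.32 months, ending in an event.

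**What each partial repair achieves.**
- Changing the 12 weeks in this sentence to 98 days repairs C (91 ≤ 98). It does not repair E (126 > 98). D passes the sentence but is then caught by the protocol's gap rule (91 > 84).
- Deleting the 12-week limit alone repairs C and E, but not D, for the same reason.
- Deleting the limit and adopting the 98-day gap from first dose repairs C, D and E. F stays censored, as in the SAP.

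**Possible number affected.** The documents give no rate of missed or non-evaluable week-6 scans. Let p be that rate (assumption), with second scans spread evenly over the 15 days 77–91 (assumption). Seven of those days (85–91) exceed 84, and 7/15 = 47%. The expected number is 70 × p × 7/15:
- p = 3%: 0.98
- p = 5%: 1.63
- p = 10%: 3.27

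This leaves out case E, where both early scans fail.

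**The case against.** The strongest reply is that the SAP already holds the better rule. Protocol 9.4 calls itself a summary, and Protocol 9 lets the SAP modify it, requiring an amendment only for major changes to the primary endpoint. PFS and TTP are secondary, so if the SAP is what gets programmed, no valid progression is lost. The SAP also applies PFS censoring to DoR, so the clash between DoR and PFS exists only in the protocol text. This stands in part. However, the SAP supplied is a draft dated September 2019 with no day, tied to a protocol of 31 July 2019, while the protocol in hand is dated 22 January 2020. The SAP does not present its rule as a departure from the protocol. An older draft cannot be assumed to override later text.

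It is also fair that every case counted above (days 85–91) would escape this sentence if its limit were 98 days. What remains then is a first adequate scan after day 98, which needs two failed scans, and for which no frequency is offered.

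The count is likely too high for the assumed rates. Protocol 7.3 asks sites to reschedule missed visits promptly and SAP 5.2.10 uses unscheduled tumor assessments, so a catch-up scan by day 84 removes the problem.

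A reader might infer that a participant with perfect imaging can be removed. That is not so when the first scan is adequate, since it is due by day 49 (case A). A punctual first scan that is read as not evaluable does not count as adequate under SAP 5.2.9, and then the rule can apply. Nor does the rule catch everyone without an early scan, because a death within 12 weeks is handled separately.

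**Conclusion.** The point holds as an unreconciled conflict between protocol and SAP, in which the protocol's literal rule discards usable data. It requires a missed or non-evaluable week-6 scan and no other adequate scan by day 84. Under the two assumptions above it affects about 1 to 3 of 70 participants, and fewer with catch-up scans. The TTP part also rests on reading the damaged word as a negative.

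Two stronger readings are not supported. The result is not a PFS of zero in the sense of an immediate failure: it is a censored time of 1 day, which removes the participant from the risk set and adds no event. The trial's conclusion on its primary endpoint is not in doubt either: ORR counts responses regardless of gaps in assessment (SAP 2.1.1), and PFS and TTP are descriptive Kaplan-Meier summaries with no hypothesis test. The matter is worth correcting because it is avoidable and because two analysts could each follow a current document and report different PFS and TTP.

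**What to change.** In the PFS and TTP cells of Protocol 9.4.1:
1. Remove the 12-week limit from the condition on having no adequate post-baseline assessment, so that it applies only when there is none at all.
2. Replace the protocol's gap rule with the SAP's 98-day rule, measured from first dose when there is no earlier adequate post-baseline scan (SAP Tables 2 and 4). Without this step, a first adequate scan on days 85–91 that shows PD stays censored at the start.
3. State that the SAP censoring rules govern PFS and TTP, and date the SAP against the current protocol.

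Before the SAP is named as governing TTP, one conflict inside it needs settling: the text of 6.2.8 treats certain early deaths as events, while Table 4 censors them.

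The cost is a short wording change in two table cells and a cross-reference. It needs no extra data, visits or participants, and leaves the primary analysis as it is.

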# 9.4.2. Safety Analyses

All safety analyses will be performed on the Safety Population.

Drug exposure will be summarized using descriptive statistics.

All AEs will be coded using the Medical Dictionary for Regulatory Activities (MedDRA). The investigator will classify the severity of AEs using the CTCAE v4.03. A treatment emergent AE (TEAE) is defined as any event that occurs for the first time during the on-treatment period or AEs that were observed prior to the start of study treatment but increased in severity during the on-treatment period. Only TEAEs with an onset date prior to date of last dose + 28 days or the date of initiation of a new anti-cancer therapy (whichever occurs first) will be tabulated in summary tables. All data will be listed. The number and percentage of participants with AEs will be summarized by MedDRA system organ class, preferred term, relationship to study intervention, and severity. A byparticipant listing will be provided for those participants who experience an SAE, including death, or experience an AE associated with discontinuation of study intervention.

#### 9.5. Interim Analyses

No interim analysis is planned for this study.

# 9.5.1. Data Monitoring Committee (DMC)

This study will not use a data monitoring committee.

## 9.5.2. Independent Central Radiological Review

An independent core imaging laboratory will be used in this study. All sites will be required to submit images to the core imaging laboratory for ICR as soon as they are performed at the site so that imaging scans may be read in real time. The requirements of submitting images will be provided to sites by the core imaging laboratory.

## 10. SUPPORTING DOCUMENTATION AND OPERATIONAL CONSIDERATIONS

## 10.1. Appendix 1: Regulatory, Ethical, and Study Oversight Considerations

## 10.1.1. Regulatory and Ethical Considerations

This study will be conducted in accordance with the protocol and with the following:

- Consensus ethical principles derived from international guidelines including the Declaration of Helsinki and Council for International Organizations of Medical Sciences (CIOMS) International Ethical Guidelines
- Applicable International Conference on Harmonisation (ICH) Good Clinical Practice (GCP) Guidelines
- Applicable laws and regulations, including applicable privacy laws.

The protocol, protocol amendments, ICF, SmPC, and other relevant documents (eg, advertisements) must be reviewed and approved by the sponsor and submitted to an IRB/IEC by the investigator and reviewed and approved by the IRB/IEC before the study is initiated.

Any amendments to the protocol will require IRB/IEC approval before implementation of changes made to the study design, except for changes necessary to eliminate an immediate hazard to study participants.

The investigator will be responsible for the following:

- Providing written summaries of the status of the study to the IRB/IEC annually or more frequently in accordance with the requirements, policies, and procedures established by the IRB/IEC.
- Notifying the IRB/IEC of SAEs or other significant safety findings as required by IRB/IEC procedures.
- Providing oversight of the conduct of the study at the site and adherence to requirements of 21 CFR, ICH guidelines, the IRB/IEC, European regulation 536/2014 for clinical studies (if applicable), and all other applicable local regulations.

In the event of any prohibition or restriction imposed (ie, clinical hold) by an applicable regulatory authority in any area of the world, or if the investigator is aware of any new information that might influence the evaluation of the benefits and risks of the investigational product, Pfizer should be informed immediately.

In addition, the investigator will inform Pfizer immediately of any urgent safety measures taken by the investigator to protect the study participants against any immediate hazard, and of any serious breaches of this protocol or of ICH GCP that the investigator becomes aware of.

#### 10.1.2. Financial Disclosure

Investigators and sub-investigators will provide the sponsor with sufficient, accurate financial information as requested to allow the sponsor to submit complete and accurate financial certification or disclosure statements to the appropriate regulatory authorities. Investigators are responsible for providing information on financial interests during the course of the study and for 1 year after completion of the study.

#### 10.1.3. Informed Consent Process

- The investigator or his/her representative will explain the nature of the study to the participant or his/her legally authorized representative and answer all questions regarding the study.
- Participants must be informed that their participation is voluntary. Participants or their legally authorized representative will be required to sign a statement of informed consent that meets the requirements of 21 CFR 50, local regulations, ICH guidelines, Health Insurance Portability and Accountability Act (HIPAA) requirements, where applicable, and the IRB/IEC or study center.
- The investigator must ensure that each study participant is fully informed about the nature and objectives of the study, the sharing of data related to the study and possible risks associated with participation, including the risks associated with the processing of the participant's personal data. The participant must be informed that his/her personal study-related data will be used by the sponsor in accordance with local data protection law. The level of disclosure must also be explained to the participant.
- The participant must be informed that his/her medical records may be examined by Clinical Quality Assurance auditors or other authorized personnel appointed by the sponsor, by appropriate IRB/IEC members, and by inspectors from regulatory authorities.
- The investigator further must ensure that each study participant is fully informed about his or her right to access and correct his or her personal data and to withdraw consent for the processing of his or her personal data.
- The medical record must include a statement that written informed consent was obtained before the participant was enrolled in the study and the date the written consent was obtained. The authorized person obtaining the informed consent must also sign the ICF.
- Participants must be re-consented to the most current version of the ICF(s) during their participation in the study.
- A copy of the ICF(s) must be provided to the participant or the participant's legally authorized representative.

#### 10.1.4. Data Protection

- All parties will comply with all applicable laws, including laws regarding the implementation of organizational and technical measures to ensure protection of participant data.
- Participants' personal data will be stored at the study site in encrypted electronic and/or paper form and will be password protected or secured in a locked room to ensure that only authorized study staff have access. The study site will implement appropriate technical and organizational measures to ensure that the personal data can be recovered in the event of disaster. In the event of a potential personal data breach, the study site shall be responsible for determining whether a personal data breach has in fact occurred and, if so, providing breach notifications as required by law.
- To protect the rights and freedoms of natural persons with regard to the processing of personal data, participants will be assigned a single, participant-specific numerical code. Any participant records or datasets that are transferred to the sponsor will contain the numerical code; participant names will not be transferred. All other identifiable data transferred to the sponsor will be identified by this single, participant-specific code. The study site will maintain a confidential list of participants who participated in the study, linking each participant's numerical code to his or her actual identity. In case of data transfer, the sponsor will protect the confidentiality of participants' personal data consistent with the Clinical Study Agreement and applicable privacy laws.

